Symptomatic hyperammonemic events, classified as hyperammonemic crises (HAC) are often triggered by acute stressors, most commonly concurrent infection, but can become a life-threatening event at any age [Lichter-Konecki 2013; Batshaw 2014]. For example, adults with late-onset OTC deficiency have become hyperammonemic after crush injury, following surgery, when on a high-protein diet, during the postpartum period, and when treated with chemotherapy, high-dose corticosteroids, valproate, or haloperidol [Lichter-Konecki 2013; Batshaw 2014]. Consistent with the Urea Cycle Disorders Consortium (UCDC), we have defined hyperammonemic crisis (HAC) in this study as an episode of signs and symptoms associated with hyperammonemia (such as frequent vomiting, nausea, headache, lethargy, irritability, combativeness, and somnolence), with documented elevated ammonia levels (≥ 100 $\mu\text{mol/L}$) and requiring medical intervention [Kent and Holt 2017; Longo and Holt 2017; Diaz 2019].

Successful rescue from an initial hyperammonemic crisis does not eliminate the chronic risk patients have for developing repeat episodes of hyperammonemia, which may present as lethargy, seizures, or coma. Regardless of the age of onset, neuropsychological complications for all individuals with OTC

Protocol: 301OTC01

deficiency typically include developmental delay, learning disabilities, intellectual disability, attention deficit hyperactivity disorder, and executive function deficits.

The current standard of care for OTC deficiency is to limit dietary protein intake and supplement the diet with a high-energy source, such as glucose [Leonard 2001]. If plasma ammonia is not stabilized by dietary restriction alone, ammonia scavengers that promote an alternative pathway of nitrogen removal can be administered [Batshaw 2001; Häberle 2012; Lichter-Konecki 2013; Häberle 2019]. Ammonia scavengers cannot, however, completely prevent individuals from having hyperammonemic crises [Batshaw 2001]. Orthotopic liver transplantation can correct OTC deficiency; however, this is limited by donor availability and is associated with significant risk of morbidity and mortality [Leonard 2004].

Thus, there remains a significant unmet medical need for a treatment that allows for sustained ammonia management and prevention of hyperammonemic crises associated with OTC deficiency.

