8.2.4.1.2 Treatment for Possible Vector-Induced Hepatitis

The investigator, in conjunction with the Ultragenyx Pharmaceutical Inc. medical lead will consider starting oral steroid treatment, per protocol, for possible vector-induced hepatitis when a subject's **ALT is greater than the ULN** and is considered by the investigator to be related to treatment with DTX301. The subject must be assessed as clinically and metabolically stable, and intercurrent illnesses (eg, viral infection) or concomitant medications known to affect transaminases, be excluded.

Repeat liver function testing for confirmation of results should be considered to inform the use of steroid treatment. If repeat testing is deemed necessary, every effort should be made to repeat the testing within 24 hours from receipt of test results indicating elevated ALT.

At any point between scheduled visits, additional, unscheduled assessment for LFTs, plasma ammonia, or any other biomarker to assess subject safety and clinical status may be performed, at the discretion of the investigator.

Changes to baseline treatment (ie, ammonia scavenger medications and protein-restricted diet) cannot occur while the subject is treated with corticosteroids or within a 2-week period of completing a corticosteroid taper.

Based on available evidence, it is expected that vector-induced hepatitis will be self-limiting. Therefore, oral prednisone (or prednisolone) will be used per the American Association for the Study of Liver Disease guidelines, with a slight modification in **Cohorts 1 to 3**:

- Week 1: prednisone 60 mg/day
- Week 2: prednisone 40 mg/day
- Week 3 and Week 4: prednisone 30 mg/day
- Week 5 and thereafter: prednisone will be tapered by 5 mg/week until liver enzymes return to baseline levels. The use of prednisone will be recorded on the appropriate page in the eCRF.

Protocol: 301OTC01

Cohort 4 (Dosing Process Optimization) will utilize an alternative regimen of corticosteroids, aiming at prophylaxis of vector-induced hepatitis. Therefore, oral prednisone (or prednisolone) will be initiated before dosing with DTX301, sustained for 4 weeks, followed by tapering as described below. Prophylactic corticosteroid regimens are in use for gene transfer therapies [Audentes 2017 Clinicaltrials.gov identifier: NCT03223194; Abeona Therapeutics 2016 ClinicalTrials.gov identifier: NCT02716246].

- At least 5 days prior to dosing: prednisone 60 mg/day

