- Study Day 1 (Week 1) through Week 4: prednisone 60 mg/day
- Study Week 5 through Week 8, tapering every 5 days:

| Taper Dose | Duration |
|----------------------|-----------------|
| 40 mg/ day | 5 days |
| 30 mg/day | 5 days |
| 20 mg/day | 5 days |
| 10 mg/day | 5 days |
| 5 mg/day | 5 days |
| 5 mg every other day | 5 days |

At any time after initiation of prophylactic corticosteroid regimen, additional assessments of plasma ammonia levels, amino acid profiles, or any other biomarker to assess subject safety and clinical status may be performed, at the discretion of the investigator and as clinically indicated.

Utilization of prednisone (or prednisolone) after dosing and after completion of the prophylactic regimen, remains available to all subjects when a subject’s ALT is greater than the ULN and is considered by the investigator to be related to treatment with DTX301. The use of prednisone (or prednisolone) will be recorded on the appropriate page in the eCRF.

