|------------------------------------------------------------------|-----------|---------------------|--------------------------------|-------------------------------|-----------------------------------------------------------------------------------------------------------------------------------------|------------|----------------|------------|----------------|------------|----------------------|----------------|------------|------------------|--------------------------------------|
| | | | IC | | OC/ HHS | OC/ HHS | IC | OC/ HHS | IC | OC/ HHS | OC (all subjects) | IC | OC/ HHS | IC | |
| Visit Type | OC | IC | Prior to DTX301 Infusion | DTX301 Dosing/ Postdose | OC/ HHS | OC/ HHS | IC | OC/ HHS | IC | OC/ HHS | OC (all subjects) | IC | OC/ HHS | IC | |
| Week | - | - | - | - | 2 | 4 | 6 | 10 | 12 | 16 | 20 | 24 | 36 | 52 | |
| Day | -35 to -1 | 0 | 1 | 1 | 14 | 28 | 42 | 70 | 84 | 112 | 140 | 168 | 252 | 364 | |
| Visit Window (Days) | - | - | - | - | ±2 | ±2 | ±2 | ±2 | ±2 | ±7 | ±7 | ±7 | ±7 | ±7 | |
| Samples for plasma ammonia (AUC ₀₋₂₄) ^{g,k} | | X ^{l,m} | | | | | X ^m | | X ^m | | | X ^m | | X ^{l,m} | |
| Amino acid panel | | X ^c | | | | | X ^c | | X ^c | | | X ^c | | X ^c | |
| AAV8 neutralizing antibody test (cell-based assay) | X | X ^c | | | | | | | | | | | | X ^c | |
| AAV8 binding antibody IgG assay (ELISA) | X | X ^c | | | | | | | | | | | | X ^c | |
| Anti-OTC antibody assay (ELISA) | | X | | | | | | | X | | | | | X | |
| Saliva, urine, and stool for viral shedding | | X ^c | | | | | X ^c | X | X ^c | X | X ^c | X ^c | X | X ^c | |
| Complete PE | X | | | | | | | | | | | | | X | |
| Targeted PE | | X | | | | | X | | X | | | X | | | |
| 12-Lead ECG | X | X | | X ^p | | | | | | | | | | X | |
| PROMIS questionnaire ^q | | X | | | | | X | | X | | | X | | X | |
| WASI-II vocabulary and matrix reasoning subtests | | X ^l | | | | | | | | | | | | | |

| Procedure | Screening | Day 0 (Baseline) | Day 1 (DTX301 Dosing) | | Treatment Period: Includes Inpatient Clinic (shaded gray) and Outpatient Clinic/HHS visits. For home visits, refer to Table 15-2. | | | | | | | | | | End of Study/ Early Withdrawal |

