| 
Version 4.0 (25 November 2021)
 | 
 • Section 3.1, Overall Study Design and Plan: Updated the priority of enrollment for Cohort 4. • Section 8.1, Rate of Ureagenesis: Removed OTC genotype from the fixed effects in the MMRM model. • Section 8.2, Plasma Ammonia Area Under the Curve from Time 0 to 24 Hours: Geometric summary statistics will be provided overall, by cohort, and for Cohorts 3 and 4 combined. A linear MMRM will provide a comparison of the logarithmic transformation of plasma ammonia AUC_{0-24hr} for each DTX301 dose vs the lowest dose and at each visit vs Baseline. Removed OTC genotype from the fixed effects and baseline results as a continuous covariate in the MMRM model. • Section 8.3.8, Baseline Disease Management: Added definitions of Responder and Complete Responder for future development. • Section 8.3.9, Dietary Protein Prescription: In addition to total daily dietary protein intake, intact food protein and medical food protein will be summarized. Counts and percentages of subjects with type of change and of subjects on unrestricted protein diet will be generated. • Section 9.4, DTX301 Vector Genome Determination and Viral Shedding: Baseline value, highest value/timepoint, and timepoint of third consecutive negative results will be provided for each subject and sample type. Median values over time by cohort and sample type will be presented in a figure. Longitudinal displays over time by cohort for each subject and sample type will be generated. • Section 13, References: Updated list of references. |

TABLE OF CONTENTS

| | |
|---|-----------|
| LIST OF ABBREVIATIONS | V |
| 1. INTRODUCTION | 7 |
| 2. STUDY OBJECTIVES AND ENDPOINTS..... | 7 |
| 3. INVESTIGATIONAL PLAN | 9 |
| 3.1. OVERALL STUDY DESIGN AND PLAN | 9 |
| 3.2. IMPLEMENTATION OF THE N-CRM MODEL | 9 |
| 3.2.1. CANDIDATE DOSES | 10 |
| 3.2.2. DEFINITION OF A DOSE LIMITING TOXICITY | 10 |
| 3.2.3. DEFINITION OF THE MAXIMUM TOLERATED DOSE | 10 |
| 3.2.4. TARGET TOXICITY RATE | 10 |
| 3.2.5. ESCALATION RULE | 10 |
| 3.2.6. N-CRM STOPPING RULES..... | 10 |
| 3.2.7. DOSE-TOXICITY MODEL..... | 11 |
| 3.2.8. NUMBER OF TOXICITIES REQUIRED BEFORE ALL DOSES ARE CONSIDERED UNSAFE | 11 |
| 3.2.9. COHORT SIZE..... | 12 |
| 3.2.10. OTHER CLARIFICATIONS..... | 12 |
| 3.3. TREATMENTS..... | 12 |
| 4. GENERAL STATISTICAL CONSIDERATIONS | 13 |
| 4.1. BASELINE AND CHANGE FROM BASELINE..... | 13 |
| 4.1.1. UREAGENESIS BASELINE | 13 |

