3.3. Treatments

Subjects will receive a single, peripheral IV infusion of DTX301, administered by qualified study personnel as designated by the investigator. The dose will be determined by the cohort and candidate dose.

Subjects in cohort 4 will be treated with the OBD defined with the assessment of the three previous dose cohorts. Subjects treated in cohort 4 (Dosing Process Optimization) will utilize an alternative regimen of corticosteroids, aiming at prophylaxis of vector-induced hepatitis. Therefore, prednisone (or prednisolone) will be initiated before dosing with DTX301, sustained for 4 weeks, followed by tapering.

The dose of DTX301 to be administered will be calculated using the subject's weight recorded at Screening. The subject's weight will be verified prior to administration of DTX301 to ensure that their current weight is within 10% of their weight at Screening.

The efficacy data will be modeled by dose (i.e. cohorts 3 and 4 will be combined, with OBD being determined as 1.0×10^{13} GC/kg). The other data will be summarized/reported by DTX301 dose/prophylactic corticosteroids (i.e. by cohort) and presented in the tables, figures and listings as follows:

- DTX301 2.0×10^{12} GC/kg
- DTX301 6.0×10^{12} GC/kg
- DTX301 1.0×10^{13} GC/kg
- DTX301 1.0×10^{13} GC/kg + Prophylactic corticosteroids

4. General Statistical Considerations

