4.1.3. Change from Baseline

All explicit references to change from baseline in this SAP refer to absolute change from baseline. Change from baseline is defined [REDACTED]

Percent change from baseline is defined [REDACTED]

If either the baseline or post-baseline value is missing, then the change from baseline and percent change from [REDACTED]

baseline value are set to missing. For each time point where change from baseline is evaluated for continuous variables, descriptive statistics will be displayed for the values at baseline, values at the given time point, and values for change from baseline at the given time point for those subjects who have data at both the baseline and the time point being evaluated.

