8.2. Plasma Ammonia Area Under the Curve from Time Zero to 24 Hours

This efficacy endpoint is defined as change from baseline in the AUC_{0-24h} of plasma ammonia at Weeks 6, 12, 24, Early Withdrawal, and End of Study (Week 52). Two samples will be collected at each visit and timepoint. One sample will be processed by the local laboratory and one sample will be processed by the central laboratory. The observed, change from baseline, and percent change from baseline in the AUC_{0-24h} of plasma ammonia will be summarized by category (i.e. central laboratory vs. local laboratory), DTX301 dose/prophylactic corticosteroids, and visit based on the SS. Change from baseline in the AUC_{0-24h} of plasma ammonia will be analyzed [redacted] [redacted] used for change from baseline in rate of ureagenesis based on the SS.

The baseline for the AUC_{0-24h} measurement is based on the hourly plasma ammonia results beginning on Day 0 and ending on Day 1 prior to DTX301 administration. AUC_{0-24h} will be calculated [redacted]

[redacted]

[redacted]

[redacted]

The rules for handling of missing data for the AUC_{0-24h} calculation are described in the [Appendices](#).

The plasma ammonia listing and summary will also include the time-normalized AUC_{0-24h} , calculated [redacted]

[REDACTED]

The following additional summary statistics will be provided (overall, by DTX301 dose/prophylactic corticosteroids and for Cohorts 3 and 4 combined) for both AUC_{0-24h} and time-normalized AUC_{0-24h} of plasma ammonia by visit: geometric mean, coefficient of variation (CV) %, geometric CV%. The mean and the standard deviation will also be provided for the logarithmic transformation of both AUC_{0-24h} and time-normalized AUC_{0-24h} of plasma ammonia.

An additional linear mixed model for repeated measures will provide a comparison of the

[REDACTED]

A longitudinal plot of plasma ammonia (as determined by central lab) will be provided by subject, including the display of the AUC_{0-24h} for the subject alongside each plot.

A longitudinal plot of plasma ammonia AUC_{0-24h} (as determined by central lab), alanine aminotransferase (ALT) level (as determined by central lab for both scheduled and unscheduled visits), and corticosteroid regimen (prednisone/prednisolone) over time (each dose taken at the visit and possibly dose modifications in-between) will also be provided by subject.

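### Cohort 4's only planned ammonia AUC0-24 baseline is on prednisone 60 mg/day, yet its two subjects are pooled with Cohort 3 in the modelled 1e13 GC/kg change, with no readable fit that leaves them out

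*SAP*

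**What the plan says.** **Pooling.** SAP 3.3 states: "The efficacy data will be modeled by dose (i.e. cohorts 3 and 4 will be combined, with OBD being determined as" 1.0 × 10^13 GC/kg. The same section reports all other data in four groups, which keep the prophylactic-steroid group separate.

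**Steroid schedule.** For Cohort 4, Protocol 8.2.4.1.2 gives "At least 5 days prior to dosing: prednisone 60 mg/day", the same dose through Week 4, and then "Study Week 5 through Week 8, tapering every 5 days", in six listed steps of 5 days. The regimen for Cohorts 1 to 3 is reactive. It is considered after dosing, when ALT exceeds the upper limit of normal and the investigator relates this to DTX301.

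**Ammonia baseline.** In Protocol Table 15-1 the AUC0-24 row, "Samples for plasma ammonia", has entries at Day 0 and Weeks 6, 12, 24 and 52, and none at Screening. SAP 8.2 says that the baseline "measurement is based on the hourly plasma ammonia results beginning on Day 0 and ending on Day 1 prior to DTX301 administration". The baseline definition in SAP 4.1.2 is blacked out.

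**Scale of the models.** SAP 4.1.3 says: "All explicit references to change from baseline in this SAP refer to absolute change from baseline". SAP 8.2 also announces an additional mixed model whose details are blacked out. The Version 4.0 entry in the SAP version log identifies it as log-scale: "A linear MMRM will provide a comparison of the logarithmic transformation of plasma ammonia" AUC0-24. That entry is used here for the form of the model only.

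**Steroids and ammonia.** Protocol Section 1 says that adults with late-onset disease have become hyperammonemic, among other circumstances, "when treated with chemotherapy, high-dose corticosteroids, valproate, or haloperidol". Protocol 3.2.4 counts steroid treatment among times of increased metabolic demand.

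**The concern.** A change from baseline is comparable across subjects only if baseline is measured under comparable conditions. Here one of the two cohorts pooled at the top dose has its baseline on high-dose prednisone and its later values off prophylaxis. The other has no planned steroid at baseline. If prednisone raises ammonia, part of the later fall in Cohort 4 is recovery from the steroid and not an effect of DTX301. That part would be credited to the 1e13 GC/kg level and would carry into its contrasts with 2e12 and 6e12.

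The ureagenesis endpoint is better protected. Under SAP 4.1.1 its baseline averages Screening and Day 1, and reverts to Screening if the two differ by 25% of the normal rate or more. Ammonia AUC0-24 has no Screening profile to fall back on. SAP 4.10 treats p-values of 0.05 or less as statistically significant unless otherwise specified, so modelled ammonia contrasts may be read as more than description.

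**Working it through.** The plan has no figure of its own to reproduce: SAP 4.9 says that the sample size does not rest on a power calculation.

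**Step 1: Cohort 4 prednisone at each AUC0-24 visit (Protocol 8.2.4.1.2, Table 15-1).** Starting at least 5 days before Day 1 means Day -4 or earlier, so Day 0 follows at least 4 days of treatment. Full dose runs to Day 28. Six 5-day steps then cover Days 29 to 58.

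| AUC visit | Planned prednisone, Cohort 4 |
|---|---|
| Day 0 to Day 1 predose | 60 mg/day |
| Week 6 (Day 42 ± 2) | 20 mg/day (Days 39-43) or 10 mg/day (Days 44-48) |
| Week 12 (Day 84 ± 2) | none; earliest visit Day 82, 82 - 58 = 24 days after the taper |
| Weeks 24 and 52 | none |

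The six steps total 30 days, while Weeks 5 to 8 span 28. Those two statements need reconciling, but the taper ends well before Day 82 on either count.

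Protocol 3.2.2 lets sites vary the timing and sequence of baseline assessments but requires no off-steroid AUC. The on-steroid baseline is therefore planned, not certain for each subject.

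**Step 2: weight of Cohort 4.** SAP 3.1 says Cohort 4 closed with 2 subjects. The final size of Cohort 3, n3, is not stated.
- n3 = 3 is an assumption: 9 subjects were enrolled at Amendment 5, in cohorts of three.
- n3 = 10 is the most that 18 subjects allow with three each in Cohorts 1 and 2: 18 - 3 - 3 - 2 = 10.
- n3 = 6 is an intermediate value.

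Under equal weighting, w = 2/(n3 + 2) = 0.40, 0.25 and 0.17.

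**Step 3: shift in the pooled estimate.** This assumes no steroid effect at follow-up and no adjustment for baseline. If prednisone raises baseline AUC by a fraction x, the pooled follow-up/baseline ratio is multiplied by (1 + x)^(-w).

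| Assumed rise x | n3 = 3 | n3 = 6 | n3 = 10 |
|---|---|---|---|
| 10% | -3.7% | -2.4% | -1.6% |
| 20% | -7.0% | -4.5% | -3.0% |
| 50% | -15.0% | -9.6% | -6.5% |

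For example, 1.20^(-0.40) = 0.930. A fall in ammonia caused by the steroid would be multiplied the other way: an assumed 10% fall gives 0.90^(-0.40) = 1.043, or +4.3%, at n3 = 3.

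On the absolute scale, again unadjusted, a rise of s shifts the mean change by -w·s. For an assumed s of 10 µmol/L in time-normalised ammonia (10 × 24 = 240 µmol·h/L in AUC0-24), the shift is -4.0, -2.5 or -1.7 µmol/L (-96, -60 or -40 µmol·h/L).

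The lower-dose groups have no planned pre-dose steroid, so on either scale the whole shift passes into the contrast with them.

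**Step 4: steroid exposure in Cohorts 1 to 3.** Protocol 1.3.1 reports liver-enzyme rises in 6 subjects from about Day 8 to Week 7. A reactive course of 60/40/30/30 mg/day by week, then 25/20/15/10/5 if tapered to zero, lasts 9 weeks or 63 days. Started on Day 8 it ends on Day 70; started on Day 49 it ends on Day 111. One course can overlap Week 6 or Week 12, but not Week 24 (earliest Day 161) or Week 52. Repeat courses could.

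**The case against.** **Redaction.** A steroid term, cohort term or sensitivity fit would be specified in SAP 4.1.2, 8.1 or 8.2, which are partly blacked out. A reader might infer that the plan contains none. The documents do not support that; they support only that none is readable. This objection stands in full.

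**Existing outputs.** A reader might also infer that Cohort 4's contribution cannot be seen. That is wrong. SAP 8.2 summarises observed values, change and percent change by dose/prophylaxis group and visit, and SAP 4.1.3 displays baseline values with each change. Geometric statistics are given by cohort and for Cohorts 3 and 4 combined. By-subject plots set ammonia against every steroid dose, and spot ammonia is also taken at Screening. What these outputs do not give is the modelled 1e13 estimate and contrasts without Cohort 4.

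**Baseline adjustment.** The shifts above assume an unadjusted model. The Version 4.0 log entry records that baseline was dropped as a covariate from the log-scale model, but the governing text is blacked out and the terms of the change-from-baseline model cannot be read. A model adjusted for baseline would shift less.

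**Size and direction.** The protocol names high-dose corticosteroids as a trigger of hyperammonemia. It does not say that ammonia rises in stable, scavenger-treated subjects. Stability is required before prophylaxis, and the ammonia limits for Day 0 and Day 1 predose (below 100 or 200 µmol/L, depending on history) restrict an extreme rise without excluding a smaller one.

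**Pooling is legitimate.** It is openly specified and matches a dose-level objective. That is a reason to keep it as the main fit, and does not argue against a check beside it.

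**Conclusion.** The point holds, as a minor one. Readable text puts an on-steroid and an unmedicated planned baseline into one modelled 1e13 GC/kg ammonia change. At Weeks 12, 24 and 52 that change, and the contrasts with lower doses, can include a fall from a steroid-affected baseline in two subjects.

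Cohort 4's share is 40%, 25% or 17% at n3 = 3, 6 or 10, and an assumed 20% rise shifts the pooled ratio by -7.0%, -4.5% or -3.0%. These figures rest on equal weighting, no baseline adjustment, an assumed rise and an assumed n3. The documents give no estimate of the rise.

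Two stronger conclusions might be inferred and are not supported. The first is that the top-dose ammonia benefit is inflated. If prednisone raises baseline ammonia, this component looks like benefit. However, reactive steroids after dosing and scavenger tapering (part of the endpoint's setting) can push follow-up ammonia up, so the net direction is uncertain. The second is that the choice of dose is affected. SAP 3.1 says the optimal biological dose had been declared with Cohort 3, so no dose decision depends on this model.

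**What to change.** Keep the pooled ammonia models in SAP 3.3 and 8.2. Beside them:

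- Report a sensitivity fit of each ammonia AUC0-24 model without Cohort 4.
- Footnote Cohort 4's AUC0-24 baseline as on-steroid wherever pooled 1e13 GC/kg ammonia estimates appear.
- State that the sensitivity fit is not steroid-free, because subjects in any cohort may receive reactive steroids after dosing.

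If a blacked-out term or fit already handles this, the sponsor need only confirm it.

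The cost is SAP wording, a footnote and extra model runs on data already held. Precision is lost in the sensitivity fit only. At equal variance the standard error of the 1e13 mean grows by sqrt((n3 + 2)/n3) = 1.29, 1.15 or 1.10 at n3 = 3, 6 or 10, that is by about 29%, 15% or 10%. For the contrast with a 3-subject group the factor is sqrt(1/n3 + 1/3)/sqrt(1/(n3 + 2) + 1/3) = 1.12, 1.04 or 1.02. With so few subjects, the fit shows whether the modelled change depends on Cohort 4; it does not estimate the steroid effect.
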